Data and Safety Monitoring Plan	Data quality and safety monitoring will occur within the research team (data quality committee). There will be an internal DSMB committee composed of [name] (Study Design and Statistical Analysis), [name] (Nutrition) and [name], PhD, MPH (Pediatric Endocrinology), in addition to our internal research team members ([name] RD; [name] PhD RD; [name]; and study manager [name], MSPH). The committee will monitor participant accrual and retention, progress, completeness of standardized measures, and attendance at intervention sessions, as well as occurrence of hypoglycemia or other adverse events. All aspects of data collection and data storage will be carefully monitored to ensure rapid detection of errors, inconsistencies or other problems. Distributions of key variables will be monitored for data quality and safety. AE and SAE, as defined by NIH, will be reported to the local site investigator and corresponding IRBs. AE/SAEs will be reviewed monthly.

1. Executive Summary

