We plan to comply with the sIRB plan by obtaining consent from UNC's Institutional Review Board. University of Cincinnati and Cincinnati Children's Hospital and Medical Center will rely on UNC's approval with sites signing an authorization/reliance agreement that will clarify the role and responsibilities of the sIRB and the relying sites. Communication between the OH site and the UNC IRB will be facilitated by the UNC study project manager, [name]. UNC Department of Nutrition and the UNC IRB will maintain the records for the authorization/reliance agreements along with documentation of the associated communication plan.

14. Data Safety & Monitoring:

Data Safety and Monitoring Plan

To ensure timely completion of the study, MPIs [name] and [name], study endocrinologists ([name] and [name]) and program manager ([name]), will constitute the study Executive Committee that will meet weekly during the first six months and bi-weekly thereafter to oversee progress, participant well-being, data quality and completion, and problem-solve as needed. A 3-member DSMB will be convened to meet three times over the course of the study via video conference call. These meetings will be held prior to the start of the study, mid-way through the study, and at the end of the study. DSMB members represent expertise in endocrinology, nutrition, and study design and statistical analysis. Prior to the start of the study, the DSMB will review and approve the final study protocol and any significant changes to the protocol over the course of the study especially as related to participant burden or safety. Midway through the study, the DSMB will meet to monitor and advise on study participant accrual and retention, progress and completeness for all standardized measurement visits and attendance at intervention sessions. Data quality will be reviewed and staff training and certification will be monitored. Adverse events will be monitored. A summary of the DSMB report will be sent to both the local site IRBs and NIDDK as part of the annual progress reports.

Members of the DSMB have been identified by area of scientific expertise (all with relevant expertise applied to T1D), are non-conflicted, and have agreed to serve:

- Pediatric Endocrinology: [name], PhD, MPH Associate Professor of Pediatrics and Epidemiology, Director, Diabetes Program, UPMC Children's Hospital of Pittsburgh

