For purposes of monitoring and reporting adverse events, the following NIH definitions will be used:

Adverse Event (AE): any unanticipated, untoward medical occurrence that may present itself during treatment or administration of an intervention, and which may or may not have a causal relationship with the treatment. Adverse events could arise from the study (e.g., breach of confidentiality) or could arise due to the population under study.

Serious Adverse Event (SAE): Any medical occurrence that results in death; is life-threatening; requires inpatient hospitalization or prolongation of existing hospitalizations; creates persistent or significant disability/incapacity, or a congenital anomaly/birth defect.

It is highly unlikely that participation in the dietary intervention will cause an AE or SAE. Should an AE occur, however, the research dietitian and study coordinator will immediately report any AE's connected to the implementation of the intervention to the study investigators, who will keep a log of AE's and SAE's. The log will also be used to provide information about AE's in annual progress reports to participating IRBs and NIDDK.

Our team will file a written report to the site IRBs in accordance with local IRB requirements, and to NIDDK. Outcomes for AE's will be monitored by the DSMB and outcome information will be entered into a log for inclusion in reports to participating IRBs and NIDDK as required. Anticipated events relative to the population under study or relative to the study (e.g., low or high blood glucose) will be noted as potential risks on the informed consent form. The DSMB will also monitor the occurrence of these events. Should any other problems or concerns arise with the data collection or intervention program, the PI or local clinical PI will be available to address these. In addition, resource

and referral listings for community services will also be provided on a routine basis as needed. Drs. [name], [name], [name] and [name] will also work extensively with the staff at each of the clinics to ensure that if adolescents need to be referred that these situations are managed in a manner consistent with clinic preferences/ policies.

The following grading scale will be used to adjudicate AE/SAEs.

Study Relatedness:	Action Taken:	Status:
1=Definitely Unrelated	0 = None	1 = Resolved
2=Possibly Related	1 = Counteractive Medication	2 = Recovered with minor sequelae

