3=Probably Related	2 = Medical/surgical intervention	3 = Recovered with major sequelae
4=Definitely Related	3 = Hospitalization	4 = Condition still present and under treatment
5=Diabetes Related; Definitely Unrelated	4 = Other (specify under comments)	5 = Condition continues to worsen
		6 = Patient died

All AEs will be reviewed by the study Data and Safety Monitoring Board to determine if an AE is related to the research project. Our team will file a written report to the site IRBs in accordance with local IRB requirements. Outcomes for AE's will be monitored by the DSMB and outcome information will be entered into a log for inclusion in reports to participating IRBs and NIDDK as required.

Anticipated events relevant to the population under study (e.g., low or high blood glucose) will be noted as potential risks on the informed consent form. The DSMB will also monitor the occurrence of these events. The study PIs will also work with the staff at each of the clinics to ensure that if participants need to be referred, these situations are managed in a manner consistent with clinic preferences/policies.

Should any other problems or concerns arise with the data collection or intervention program, the PI or local clinical PI will be available to address these.

15. Privacy & Confidentiality

In-person recruitment will occur in the diabetes clinics by study personnel. Study visits will occur in private settings or on secure videoconference platforms. Unencrypted messaging will only occur between study personnel and parents reminding them of study sessions, encouraging them to complete questionnaires or other study activities, and only if they consent. Encrypted e-mails and text messages will be sent to minors to encourage and remind them.

To minimize the risk of loss of confidentiality, all information related to study subjects will be confidential and kept in a locked cabinet or in password-protected computer files, in compliance with NIH and HIPAA requirements as detailed in NIH Notice OD-020 issued December 30, 2004.

Each participant will be assigned a unique study identification (ID) number. Participants will be identified on all study-related documents only by their study ID numbers. The roster containing the unique identifying number and direct participant identifiers will be kept in a local password-protected database on a secure network drive at the clinical sites.

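### The safety rules contradict each other on whether non-serious glucose events are logged as adverse events, who reports them, and how and when their relatedness is judged

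*Combined protocol and SAP*

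**What the plan says.** **Definition.** Section 14, Adverse Events, defines an AE as "any unanticipated, untoward medical occurrence that may present itself during treatment" and does not require a causal link. The next sentence widens it: "Adverse events could arise from the study (e.g., breach of confidentiality) or could arise due to the population under study". A later sentence begins "Anticipated events relative to the population under study or relative to the study (e.g., low or high blood glucose" and says that such events will be named as risks on the consent form. The DSMB is also to monitor how often they occur. The SAE definition has no such limit to unanticipated events.

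**Reporting.** In Section 14 the dietitian and coordinator "will immediately report any AE's connected to the implementation of the intervention" to the investigators, who keep the log of AEs and SAEs. That log supplies the annual reports to the IRBs and NIDDK. The Data and Safety Monitoring Plan row of the synopsis has AEs and SAEs reported to the site investigator and IRBs, with no condition about connection to the intervention. It also speaks of hypoglycemia *or other* adverse events.

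**Relatedness.** Section 14 states: "All AEs will be reviewed by the study Data and Safety Monitoring Board to determine if an AE is related" to the research project. Codes 1 to 4 run from definitely unrelated to definitely related. The fifth code is "5=Diabetes Related; Definitely Unrelated".

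**Timing.** The synopsis states "AE/SAEs will be reviewed monthly". Section 14 states "A 3-member DSMB will be convened to meet three times over the course of the study": before the start, mid-way and at the end.

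**The concern.** The intervention changes when adolescents with type 1 diabetes eat and how they spread carbohydrate over the day. The protocol accepts that this can move glucose. Section 12 lists an unanticipated effect of the diet on glycemic control among the physical risks, and adds that medical management may need adjusting as eating patterns change. Glucose events are therefore the harm that the AE system most needs to handle well.

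As written, site staff cannot follow all the rules at once, and several of them point the same way. They leave a non-serious glucose event out of the AE log, or they invite a coder to mark it unrelated. The pilot could then report few related AEs partly because of its definitions. That count would go to the IRBs and NIDDK and would inform the planned larger trial.

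**Working it through.** No sample size, power or alpha figure is involved, and the plan states no figure to reproduce. The check sets the rules side by side and then counts meetings and months.

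**1. Is a non-serious low or high glucose an AE?**

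| Text | Answer |
|---|---|
| Section 14, AE definition, first sentence (unanticipated events), with glucose named later as anticipated | No |
| Section 14, AE definition, second sentence (events due to the population) | Yes |
| Synopsis, hypoglycemia listed with other adverse events | Yes, for hypoglycemia |

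The three do not agree. If the first governs, the event is not an AE, so the duties to log it and to judge its relatedness do not apply.

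**2. Which AEs do staff report?** Section 14 names those connected to the intervention; the synopsis names AEs and SAEs without condition. Section 14 also gives the DSMB the task of judging relatedness for all AEs. If staff apply the Section 14 sentence as a filter, those delivering the intervention make a relatedness judgment before the body assigned to make it.

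**3. Can the scale record a plan-related glucose event?** Such an event is both diabetes related and study related. Codes 2, 3 and 4 can record the study link but have no place for the diabetes link. Code 5 records the diabetes link and fixes the study link at definitely unrelated. No single code records both.

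**4. When is relatedness judged?**
- DSMB meetings between start and end: 3 in total − 1 before the start − 1 at the end = 1.
- Intervention window in Section 16, December 2021 to May 2023: 1 + 12 + 5 = 18 calendar months.
- Monthly review over that window: about 18 reviews, against 1 mid-study DSMB meeting and 1 at the end.

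The monthly review therefore cannot be the scheduled DSMB meetings, and no other body is named for it. The synopsis describes both a research-team data quality committee and a DSMB committee that lists research team members, so the reader cannot tell which is meant. No route is described by which AEs or SAEs reach the DSMB between meetings.

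**5. One event traced through.** Take a non-serious low during the intervention, reported to the dietitian at the next session. The hypoglycemia instrument records it. Under the literal Section 14 definition it stops there as far as AE handling goes. Under the synopsis it is an AE and is reported. If it is treated as an AE, Section 14 may still hold it back unless staff think it connected. If it is passed on, the coder must choose between code 5 and codes 2 to 4. At each step the outcome depends on which sentence is followed.

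**The case against.** The strongest reply is that hypoglycemia is watched closely whatever the AE definition says. It is asked about at each visit and dietitian session (synopsis, Safety Evaluations; Section 12). The instrument covers the time since the last session (Section 8c), and the questionnaire is marked across the measurement schedule in Section 8. Participants are asked to notify severe events within 48 hours (Section 12). The DSMB is told to monitor low and high glucose. The Executive Committee, which includes the study endocrinologists, meets weekly for six months and then bi-weekly, with participant well-being in its remit. All of this stands, and it rules out four stronger readings that a reader might infer.

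- *That the plan drops glucose events.* It does not drop hypoglycemia from capture. The protection is weaker for hyperglycemia, for which no comparable structured query is described.
- *That staff pass on only connected AEs.* Section 14 does not say only. Its sentence can be read as a rule about which events are reported at once, and the synopsis has no filter. The supportable finding is a conflict.
- *That every glucose event could be missing from the log.* A glucose event that meets a seriousness criterion is an SAE, and SAEs are logged. The possible loss is confined to non-serious events.
- *That safety oversight could wait nine months.* Half of 18 months is 9, but this assumes that mid-way means the midpoint of the intervention window and that nobody reviews AEs between DSMB meetings. The monthly review and the Executive Committee contradict the second assumption.

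It is also fair that code 5 can be read as a subtype of unrelated and that codes 2 to 4 remain usable, so miscoding is invited rather than forced.

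What the reply does not answer is the handling of events after capture. Asking about a low does not make it a logged, adjudicated and reported AE. The sentence on DSMB monitoring of anticipated events names no log, form, relatedness judgment or schedule.

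**Conclusion.** The concern holds as an internal contradiction with a limited reach. The rules disagree on whether non-serious glucose events are AEs, on which AEs staff report, and on how often AEs are reviewed. The relatedness scale cannot record an event as both diabetes related and study related. The consequence is possible under-logging, under-adjudication and under-reporting of non-serious glucose events. Capture of hypoglycemia, handling of serious events and the glycemic outcome analyses are not affected.

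The share of events affected cannot be computed, because the documents give no expected event rate and do not say which reading staff will follow. The conclusion rests on reading *unanticipated* in the AE definition and *anticipated* in the later sentence in their ordinary, opposite senses. The 18-month count uses Section 16; the synopsis gives an earlier end of data collection (October 2021) that cannot be squared with that window. The point should be corrected because participants are minors, the pilot's safety record will inform a larger trial, and the correction is cheap.

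**What to change.** 1. Delete *unanticipated* from the AE definition in Section 14, so that it agrees with its own second sentence and with the synopsis.
2. State that staff report and log all AEs, including the glucose events already collected on the hypoglycemia instrument, before anyone judges relatedness. Make the Section 14 reporting sentence match the synopsis.
3. Remove code 5 and add a separate diabetes-related yes/no field, so that codes 1 to 4 carry study relatedness alone.
4. Reconcile the monthly review in the synopsis with the three DSMB meetings in Section 14. Name the body that does the monthly review, and say how its results and any SAEs reach the DSMB between meetings.

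The cost is protocol wording and one form field. The downside is a longer AE list, much of it expected glucose events, which can be tabulated separately in reports by means of the new field.
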